14 OTHER STUDY ELEMENTS

14.1 INVESTIGATORS AND PATIENT POPULATION

The Principle Investigator (PI) for this study is [name] from the Canela Clinic in La Romana, Dominican Republic.

Subjects for this study will be recruited from the PI’s practice, will have been diagnosed with BPH and scheduled for surgery (Phase 1 Acute) or would otherwise be treated surgically or with other minimally invasive BPH treatment (Phase 2 – Optimization).

14.2 STATISTICAL ANALYSIS

Descriptive statistics will be calculated and reported for study variables, as appropriate. Continuous variables (e.g., symptom score, uroflowmetry, quality of life assessments) will be summarized using statistics such as means, standard deviations and absolute change from baseline. Categorical variables (e.g., adverse events) will be summarized as frequency

distributions. Adverse events and technical observations will be reported by frequency of occurrence, severity and relationship to the vapor treatment device.

All subjects enrolled in this study (including those withdrawn from the study or lost to follow-up) will be accounted for and documented.

14.3 UNSCHEDULED FOLLOW-UP VISITS

If subjects are seen for unscheduled/interim visits because of an AE, appropriate Clinical Report Form(s) (CRF(s)), including the AE CRF, will be completed, if applicable.

14.4 LOST TO FOLLOW-UP

If a subject fails to comply with follow-up evaluations, the investigational site must make repeated attempts (at least three) to contact the subject. Each attempt to contact the subject and the method used (e.g., telephone contact, registered letter) must be documented in the subject's records. A last unsuccessful attempt to contact a subject must be documented by a returned, registered letter sent to the subject.

If a subject misses one of the follow-up evaluations but is present at the subsequent follow-up, the subject can be readmitted into the study and queried retrospectively for basic information; however, the missed evaluation must be documented on a Protocol Deviation CRF.

14.5 SUBJECT WITHDRAWAL FROM STUDY

14.5.1 Voluntary Withdrawal

A subject may voluntarily withdraw from the study at any time. If a subject officially withdraws from the study, the investigator must ensure that there is documentation for the reason for the withdrawal. If the subject had an AE, the subject should be followed until the resolution of the AE, if possible.

14.5.2 Withdrawal Due to Exclusion Criteria

A subject may be withdrawn from the study if subject is later found to not meet study selection criteria.

14.5.3 Involuntary Withdrawal

A subject may also be withdrawn from the study at the discretion of the investigator (e.g., for non-compliance with medical advice).

14.6 END OF STUDY

Subjects may be exited from the study at the end of the study (i.e., study discontinuation by the Sponsor) or when the subject has completed the 5 year follow-up visit. An End of Study CRF will be completed at the time of study completion or discontinuation.

14.7 DESCRIPTION OF TESTS AND EVALUATIONS

14.8 SUBJECT QUESTIONNAIRES

All questionnaires are self-administered and will be completed at baseline and at each follow-up visit. Questionnaires completed at baseline will be compared to those completed at each follow-up visit to assess any effect of treatment. The following assessments will be administered.

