Purpose:	To evaluate the effect of the NxThera BPH Rezūm System on prostate tissue in subjects suffering from LUTS symptoms secondary to benign prostatic hyperplasia (BPH).
Study Design:	
This study is a single center study. It will be carried out in two phases on subjects with benign prostatic hyperplasia.
 
Phase 1: Acute study - In-vivo treatment of the prostate in subjects scheduled to have a surgical TURP or full excision of the prostate. Prostate tissue will be excised after treatment as part of the planned surgery. There is no follow up.
 
Phase 2: Optimization study - Subjects with BPH symptoms will be treated with the Rezūm device with a range of thermal energies (as measured by calorie output) to optimize the setting for maximum lesion size with minimal intra and post procedure discomfort. The lesion size and ablated tissue resorption rate will be followed post-procedure via MRIs.

Enrollment:	
Phase 1: Up to 20 BPH subjects scheduled for surgical removal of the BPH tissue
 
Phase 2: Up to 15 BPH subjects suffering from BPH symptoms.

Target Subject Population:	
 • Male subjects \geq 45 years of age who have symptomatic / obstructive symptoms secondary to BPH requiring surgical intervention.
Follow-up:	
Phase 1 – Acute, no follow up
 
Phase 2 – 1 day, 1 week, 1 month, 3 months, 6 months, 12 months, and annually thereafter up to 5 years.

Phase 1 Endpoint	Lesion size and characteristics as evaluated using Tetrazolium Chloride (TTC) stain and histopathologic evaluation of representative samples.
Phase 2 Endpoints	
Lesion characterization via MRI
 
Intra and post procedure discomfort
 
Catheterization post procedure
 
The change (improvement) from baseline in International Prostate Symptom Scores (IPSS) at day 1, week 1, month 1, months 3,6 and 12, and annually thereafter up to 5 years

CONFIDENTIAL: Contains Proprietary Information

Study and Data Management:	Libra Medical, Inc. [name] [contact] [contact] Email: [contact]
Study Monitors:	Libra Medical, Inc. [name] [contact] [contact] Email: [contact]
Sponsor:	NxThera Inc [name] [contact]

TABLE OF CONTENTS

1	BACKGROUND.....	8
2	SUMMARY DEVICE DESCRIPTION.....	8
3	SUMMARY OF PROCEDURE	9
4	PHASE I ACUTE STUDY DESIGN.....	12
5	PHASE 2: OPTIMIZATION STUDY	13
6	STUDY PROCEDURES	15

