5 PHASE 2: OPTIMIZATION STUDY

5.1 STUDY OBJECTIVE

The objectives of the Phase 2 study are:

Optimize the effectiveness of the BPH Rezūm System and assess the effect of treatments with different caloric values, including an assessment of subject comfort during the procedure and post-procedure

Further document the safety and post-operative effects of the Rezūm System in the treatment of obstructive BPH.

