5.2 STUDY DESIGN

In this Phase 2 study, up to 15 subjects with LUTS secondary to BPH requiring surgical treatment will be treated with the Rezūm System. Treatment is ≤ 10 seconds per treatment. The power and water flow rate settings may be adjusted slightly to minimize pain and swelling to the subjects while maximizing the treatment area (e.g., lesion size). The power setting will be between 175W and 250W with a concomitant adjustment to the water flow rate of 2.7 ml/min to 5.0 ml/min. The actual power output will be recorded. For all the treatment settings, adverse and subject responses will be collected. The range of acceptable power setting have been determined in bench-top, animal studies, testing on extirpated human prostate to create lesions of a size that is adequate to treat the BPH tissue. The unknown factor that will be evaluated in this Phase 2 study is the acute response(s) to the different treatments in terms of procedural and post procedural discomfort. If the subjects are able to tolerate the higher caloric treatments, those treatments will be used in subsequent subjects. If the subjects are not able to tolerate a particular caloric treatment, the lower caloric treatment will be used in subsequent subjects.

The standard Rezūm treatment following the IFU will be followed. Information regarding the vapor needle configuration, treatment settings, treatment medications, pain or discomfort during treatment, post-treatment catheterization requirements, and the type and severity of any short term irritative or urinary obstructive symptoms will be collected. Information regarding the subjects' symptomatic response and uroflowmetry characteristics will be collected at baseline and in follow-up evaluations conducted with each subject. Any adverse events will be evaluated at each visit. Lesion characteristics and treated tissue resorption rate will be measured by gadolinium enhanced MRI imaging techniques performed post-procedure at specified intervals.

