5.3 OPTIMIZATION ENDPOINTS

5.3.1 Endpoint 1: Intra-procedure Pain

Procedural pain will be assessed using the Wong Baker scale. Subjects will be asked to rate the level of pain and discomfort during the treatment.

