6.2 SCREENING AND BASELINE EVALUATIONS

The following evaluations will be completed for all study candidates who have provided a written informed consent:

- Complete general medical and genitourinary history (including any previous treatment for LUTS; if pharmacologic, name of drug(s) as well as dosage) and duration of subject's BPH symptoms.**
- Blood analysis:**
 - Complete blood cell count (CBC)**
 - Blood urea nitrogen (BUN)**

- Serum creatinine
- Serum prostate-specific antigen (PSA) level
- Electrolytes
- **Uroflowmetry:**
 - Voided volume (must be ≥ 125 mL or test must be repeated)
 - Total time of voiding
 - Peak flow rate (Q_{max}; also known as PFR)
 - Average urinary flow rate
 - Post-void residual urine volume (PVR; may be measured by either ultrasound or catheterization but the same method must be used pre- and post-treatment)
- **Urinalysis**
 - Urine culture, if indicated
 - Subject questionnaires:
 - International Prostate Symptom Score (IPSS)
 - BPH Impact Index (BPHII)
 - International Index of Erectile Function (IIEF)
 - Male Sexual Health Questionnaire Short Form (MSHQ-EjD Short Form)
 - Prostate volume (PV), length and width, as measured by TRUS
 - Confirmation of function of detrusor muscles via urodynamics
- **Subjects must undergo a “washout” period of 6 months if they have been on:**
 - 5-alpha reductase inhibitor
 - Subject must undergo a “washout” period of 2 weeks if they have been on:
 - alpha blockers
 - antidepressants
 - anticholinergics
 - androgens
 - gonadotropin-releasing hormonal analogs
 - Subject must undergo a “washout” period of 1 week if they have been on:
 - Beta-blockers
 - Antihistamines
 - Anticonvulsants
 - Antispasmodics
 - Unless subjects have been on a stable dosing for the last 6 months (i.e. no changes)

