6.5.1 Scheduled Follow-up Visits

Table 6-2: Schedule of Visits

	Baseline Pre-Op	1 day	1 week	1 month	3 month s	6 month s	1 year	Annual (2-5 years)	Unsched uled
IPSS	√	√	√	√	√	√	√	√	optional
BPH Impact Index	√			√	√	√	√	√	optional
EQ5D	√			√	√	√	√	√	
Sexual function (IIEF)	√			√	√	√	√	√	optional
MSHQ-EjD Short Form	√			√	√	√	√	√	optional
Subject Satisfaction Questionnaire			√	√	√	√	√	√	optional
Subject Pain Assessment		√	√	√	√	√			
Uroflow (Qmax + PVR)	√		√	√	√	√	√		optional
Urodynamics	√								
Prostate specific antigen (PSA)	√				√	√	√	√	
Prostate Volume	√				√	√	√	√	
Cystoscopy	√		√						
MRI	option al		√	√	√	√			
Adverse event(s)		√	√	√	√	√	√	√	√
Medication(s) used	√	√	√	√	√	√	√	√	√

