14.8.14 Wong Baker Pain Scale

The Wong Baker scale is a validated measurement instrument intended to measure the amount of pain that a patient feels which ranges across a continuum from none to an extreme amount of pain. The pain scale is shown in pictorial form instead of a line. Each subject selects the response that he feels best represents his perception of his then current pain level.

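### Post-procedure discomfort is a Phase 2 endpoint, but no pre-treatment pain rating is scheduled, so the pain scale cannot separate pre-existing from treatment-related discomfort

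*Combined protocol and SAP*

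**What the plan says.** The synopsis names "intra and post procedure discomfort" among the Phase 2 endpoints. Section 5.1 sets an objective "including an assessment of subject comfort during the procedure and post-procedure". Section 5.2 describes the unknown to be studied as "the acute response(s) to the different treatments in terms of procedural and post procedural discomfort". In the numbered endpoint list of 5.3, only pain during the procedure appears. Section 5.3.1 assigns it the Wong Baker scale and adds: "Subjects will be asked to rate the level of pain and discomfort during the treatment".

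The row "Subject Pain Assessment" in Table 6-2 is ticked from day 1 to month 6 and blank at baseline. Under "Subject questionnaires", section 6.2 lists the IPSS, the BPH Impact Index, the IIEF and the MSHQ-EjD, and no pain scale.

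Section 14.8 opens with "All questionnaires are self-administered and will be completed at baseline and at each follow-up visit" and says that follow-up will be compared with baseline to assess treatment effect. The Wong Baker scale is described at 14.8.14: "Each subject selects the response that he feels best represents his perception of his then current pain level". Section 14.2 plans descriptive summaries, including change from baseline for continuous variables. It does not name pain.

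**The concern.** The Wong Baker scale, as 14.8.14 describes it, records how much pain the subject has now, whatever its source. The subjects are symptomatic men judged to need invasive treatment. Section 14.8.4 itself recognises that BPH symptoms can cause physical discomfort, and sections 5.4 and 5.5 do not exclude men with pre-existing pain as such.

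There is no control group to show the background level, so each man's own pre-treatment score is the only reference on this scale. Without it, a non-zero score at week 1 or month 3 could be a lasting effect of the procedure, the condition he came with, or both. A pre-treatment rating cannot be collected once treatment has been given.

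The same reference would help safety reporting. Section 7.1 defines an adverse event as a change from the subject's baseline condition. Section 7.2 exempts procedure-related pain only up to 72 hours and only where it leads to no intervention or unplanned hospital stay. Section 7.3 lists chronic pain at the site as an anticipated event.

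**Working it through.** The plan gives no alpha, power, effect size or assumed pain distribution, so there is no figure to reproduce. The check compares the schedules.

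| Item | Baseline | Day 1 | Week 1 | Months 1, 3, 6 | Month 12 | Unscheduled |
|---|---|---|---|---|---|---|
| Pain, Table 6-2 | blank | yes | yes | yes | blank | blank |
| Pain, Table 6-1 | table covers follow-up only | yes | yes | yes | yes | optional |
| Pain, section 6.2 | not listed | – | – | – | – | – |
| BPH Impact Index, Table 6-2 | yes | no | no | yes | yes | optional |

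1. **Is the blank baseline cell an extraction fault?** Probably not. Section 6.2 is a separate list and also omits pain.
2. **What can be computed?** Table 6-2 schedules 0 ratings before treatment and 5 after it (day 1, week 1, months 1, 3 and 6). Change is follow-up score minus baseline score, and the second term is missing for all of the up to 15 subjects. The change from baseline in 14.2 is therefore unavailable for pain. So is the comparison in 14.8, if that rule covers the scale.
3. **Does another baseline measure fill the gap?** In part. The BPH Impact Index touches on physical discomfort and is given at baseline. It is a different instrument, cannot be subtracted from a pain score, and is not given at day 1 or week 1.
4. **Where does the gap matter?** Pain during a procedure done without anesthesia, and pain the day after, is likely to come mostly from the procedure. From week 1 to month 6 the procedural part should fade, and background discomfort could make up more of the score.
5. **Illustration of size, by assumption only.** Suppose 3 to 6 of 15 men carry 2 scale units of background pain that adds in full to procedural pain and stays constant.
   - Background part of the overall mean: 3 × 2/15 = 0.4 to 6 × 2/15 = 0.8 units.
   - If 2 or 3 men share a setting and one of them is such a man: 2/3 ≈ 0.7 to 2/2 = 1.0 unit in that setting's mean.

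   The documents supply none of these inputs except the 15. The results follow directly from what was assumed.

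Two related discrepancies emerge. Table 6-1 requires a pain assessment at 12 months and allows one at unscheduled visits, while Table 6-2 shows neither. Wong Baker is named only for procedural pain in 5.3.1; both tables leave the follow-up pain instrument unnamed.

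**The case against.** A reader might infer that the plan counts pre-existing discomfort as caused by the treatment. The documents do not support this. Section 14.2 is descriptive and gives no attribution rule for pain scores. Causality is judged only for adverse events: 7.1 leaves out conditions present at enrollment unless they worsen, and 7.7 lets the investigator attribute an event to underlying disease. The most that can be said is that the two sources are not separable on the scale.

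A reader might also say that the schedule flatly contradicts 14.8. That depends on calling Wong Baker a questionnaire. Section 14.8.14 describes it as a pictorial measurement instrument, and 14.8 also houses MRI, necropsy and uroflow. The blanket rule is loose in any case: the satisfaction questionnaire has no baseline, and several questionnaires are skipped at day 1 and week 1. The contradiction is conditional, but the gap exists without it. Satisfaction with a treatment cannot be rated beforehand; pain can.

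A third inference is that energy settings would be chosen wrongly. Section 5.2 moves between settings on whether subjects tolerate treatment and concerns the acute response. No rule uses mean pain per setting or scores at months 1 to 6.

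Finally, baseline discomfort is not wholly unrecorded. The medical and genitourinary history in 6.2 and the BPH Impact Index capture some of it, and 5.5 excludes several painful conditions, such as active urinary infection and bladder stones. This lowers the likely size of the problem. It does not supply a reference value on the scale used for follow-up.

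**Conclusion.** The point holds as a gap in measurement. A stated Phase 2 endpoint has no within-subject reference in a study with no control group, and the reference cannot be obtained later. The firm part rests on the schedules alone: no pre-treatment pain rating, and so no change score for any subject. The size is unknown. The 0.4 to 0.8 and 0.7 to 1.0 unit figures show only what the stated assumptions would imply, and would be smaller if background pain were rarer, milder or relieved by treatment.

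The effect on the numbered endpoint in 5.3.1, pain during the procedure, is likely small. The consequence falls mainly on reading the follow-up scores from week 1 to month 6. This is an inexpensive improvement to a small descriptive study, and the gap does not undermine the study's other endpoints.

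**What to change.** - Add one pre-treatment pain rating to 6.2 and to the Baseline column of Table 6-2, on the scale used at follow-up. Take it before any of the pre-procedure medication described in 6.4 and, if it falls at the same visit, before baseline cystoscopy and urodynamics.
- Name the instrument for the follow-up pain assessment in Tables 6-1 and 6-2, and say in 14.8 whether its baseline rule covers that instrument.
- In 14.2, state that post-procedure pain is reported as change from the pre-treatment rating alongside the raw score. Both are needed: if the two ratings correlate weakly, the change is noisier than the raw score.
- Reconcile the pain rows of Tables 6-1 and 6-2 for the 12-month and unscheduled visits.

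The cost is one single-item form per subject, at most 15 in all, plus wording changes. Treatment, sample size and number of visits are unaffected.

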4 PHASE I ACUTE STUDY DESIGN

This study will be conducted in two phases. The phases will run consecutively. Both phases are part of a single arm, single center study.

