5.4 INCLUSION CRITERIA

- 1. Male subjects \geq 45 years of age who have symptomatic / obstructive symptoms secondary to BPH requiring invasive intervention.**
- 2. IPSS score of \geq 15.**
- 3. Qmax: Peak flow rate \leq 15 ml/sec.**
- 4. Post-void residual (PVR) $<$ 300 ml.**
- 5. Prostate transverse diameter $>$ 30 mm.**
- 6. Prostate volume between 20 to 120 gm.**
- 7. Voided volume \geq 125 ml.**
- 8. Subject able to complete the study protocol in the opinion of the Principal Investigator.**
- 9. Subject must be willing to undergo the procedure without anesthesia.**

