6 STUDY PROCEDURES

6.1 SUBJECT ENROLLMENT

Only subjects who meet the inclusion/exclusion criteria will be eligible to participate in the study. It is recommended that only subjects that live within 90 minutes of driving distance from the study site be selected as participants in the study due to the study follow-up requirements.

Once it is determined that a subject meets the enrollment criteria (except for the use of the concomitant medication), the subject will be given an informed consent to read. Subjects that were on BPH medication will then go through a washout period. If the subject successfully goes through the washout period and still meets the selection criteria, the subject will be considered enrolled and assigned an enrollment ID.

The Principal Investigator (PI) or study coordinator will review the informed consent with the subject to be sure the subject completely understands the meaning of the consent. Upon completion, the subject will be given an opportunity to sign the informed consent. A subject will be considered officially enrolled only if treatment with the NxThera Rezūm System is attempted.

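### In Phase 2 the only scheduled pre-treatment IPSS both admits the subject and, as written, serves as the Endpoint 4 baseline, so part of the uncontrolled change will be regression to the mean

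*Combined protocol and SAP*

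**What the plan says.** - **Entry.** Section 5.4, item 2, requires "IPSS score of \geq 15".
- **Pre-treatment measurement.** Section 6.2 treats screening and baseline as one set, under the title "SCREENING AND BASELINE EVALUATIONS", and IPSS is in that set. Table 6-2 has a single pre-treatment column, "Baseline Pre-Op", with one tick for IPSS.
- **Endpoint.** Endpoint 4 (section 5.3.4) is the change in IPSS from baseline. Table 6-2 collects IPSS at day 1, week 1, months 1, 3 and 6, year 1 and annually in years 2 to 5, which makes ten scheduled post-procedure readings.
- **Control.** Section 4 states: "Both phases are part of a single arm, single center study".
- **Analysis.** Section 14.2 is descriptive. It reports continuous variables, symptom score among them, by "means, standard deviations and absolute change from baseline".
- **Interpretation.** Section 14.8 goes further: "Questionnaires completed at baseline will be compared to those completed at each follow-up visit to assess any effect of treatment".
- **Nearest safeguard.** Section 6.1 has men on BPH medication re-checked before enrollment: "If the subject successfully goes through the washout period and still meets the selection criteria".

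No sentence defines which IPSS reading is the baseline. The plan describes no replicate baseline, external comparator or adjustment for regression to the mean.

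**The concern.** A single IPSS reading is the man's usual score plus day-to-day variation. Among men admitted because the reading reached 15, that variation is on average upward. The next reading lacks this upward selection, so the group mean falls without any treatment. If the qualifying reading is also the baseline, the fall enters Endpoint 4 as improvement, and it does so at each of the ten follow-up readings.

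A concurrent control group would show the same fall and allow it to be subtracted. Here there is none, and the wording in 14.8 invites the reader to credit the whole change to the device. This is separate from drug washout, because it applies equally to men who never took BPH medication.

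**Working it through.** The plan gives no expected change, SD, reliability or sample-size derivation, so there is no figure of its own to reproduce. The check asks how large the spurious fall could be.

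**Inputs from the documents:** cut-off 15; up to 15 subjects; one pre-treatment IPSS; no control arm.

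**Assumed inputs, not in the documents:** mean IPSS before the cut-off is applied, 15 to 21; SD 5 to 7; test-retest correlation r, 0.7 to 0.9, taken as the same at every visit; approximate normality.

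**Formula.** With no treatment effect, the expected fall from a qualifying reading X1 to a later reading X2 is

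E(X1 − X2 | X1 ≥ 15) = (1 − r) × SD × λ, where λ = φ(z) / (1 − Φ(z)) and z = (15 − mean) / SD.

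| Mean | SD | r | z | φ(z) | 1 − Φ(z) | λ | Spurious fall |
|---|---|---|---|---|---|---|---|
| 15 | 7 | 0.7 | 0 | 0.3989 | 0.5000 | 0.798 | 0.3 × 7 × 0.798 = 1.68 |
| 18 | 7 | 0.7 | −0.429 | 0.3639 | 0.6659 | 0.5465 | 0.3 × 7 × 0.5465 = 1.15 |
| 21 | 5 | 0.9 | −1.2 | 0.1942 | 0.8849 | 0.219 | 0.1 × 5 × 0.219 = 0.11 |

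The first and last rows are the extremes of the assumed range, so the bias is about 0.1 to 1.7 points.

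**Comparison with sampling error.** The variance of the change among selected men is (1 − r)² × SD² × [1 − λ(λ − z)] + SD² × (1 − r²).

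- Mean 18, SD 7, r 0.7: 0.09 × 22.89 + 49 × 0.51 = 27.05. The SD of change is 5.20 and the standard error with 15 men is 5.20 / √15 = 1.34. The bias of 1.15 is 0.86 standard errors.
- Mean 15, SD 7, r 0.7: 0.09 × 17.81 + 24.99 = 26.59. The SD is 5.16 and the standard error 1.33. The bias of 1.68 is 1.26 standard errors, inside a 95% half-width of about 2.145 × 1.33 = 2.9.

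**Sensitivity.** Mean 12, SD 7 and r 0.6 give 3.1 points. Under those inputs only about a third of candidates would reach 15.

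**Effect of a second, ungated baseline.** Let X2 be a reading taken after qualification and not used for eligibility, and X3 a follow-up reading. If the day-to-day errors are independent, X2 and X3 have the same expectation given X1 ≥ 15, so E(X2 − X3 | X1 ≥ 15) = 0. A simulation with no treatment effect gave 0.0.

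**Effect of the post-washout re-check.** The same simulation used mean 15, SD 6, r 0.75, whole-number scores from 0 to 35, and joint selection on Qmax (assumed mean 12, SD 4, r 0.7). Using the qualifying score as baseline gave a spurious fall of 1.13. The formula gives 0.25 × 6 × 0.798 = 1.20; rounding to whole scores moves the effective cut-off to 14.5. When the second reading also had to pass the cut-off, 0.73 of the 1.13 remained.

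**The case against.** **The premise is inferred.** No sentence says that the qualifying score is the baseline. Section 6.1 has eligibility judged before the consent form is given, apart from concomitant medication, while section 6.2 places the screening and baseline evaluations after consent. Men who wash out may have two readings. This stands as a limit: the claim is about what the schedule provides. Table 6-2 offers one pre-treatment IPSS, and nothing designates another. The re-check covers only men on BPH medication and re-applies the same cut-off, so it leaves much of the bias.

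**Nothing in the plan depends on it.** There is no hypothesis test, success threshold or performance goal. Section 5.2 moves between settings on tolerability, and the cut-off is the same for every setting. This stands too. A reader might infer an inflated false-positive rate or a distorted choice of setting; the documents support neither. What remains is a biased descriptive mean with a causal phrase attached.

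**It is not the only efficacy result.** A reader might infer that the study's whole efficacy evidence is compromised. It is not. Endpoint 3 is MRI lesion size, and the BPH Impact Index, EQ5D and prostate volume are also followed. Lesion size, procedural pain and catheterization are unaffected.

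**Qmax should not be put on the same footing.** Entry also requires "Qmax: Peak flow rate \leq 15 ml/sec", so the descriptive change in Qmax carries the same kind of bias. But Qmax is not a named Phase 2 endpoint, and the sentence in 14.8 concerns questionnaires only. No text calls a flow change an effect of treatment.

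**The bias is small and rests on assumptions.** Agreed. The upper figure of 1.7 needs a mean before selection equal to the cut-off, so that half of candidates would fail it.

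**Conclusion.** The point holds for IPSS as a cheap improvement. As the schedule is written, Endpoint 4 uses a baseline selected for being high, with no control arm to remove the resulting fall. The direction is certain for any test-retest correlation below 1: it favours the device. The size cannot be found from the documents. Under the assumed inputs it is about 0.1 to 1.7 points, at most about 1.3 standard errors with 15 men. A reader might infer that regression to the mean could account for a large IPSS improvement; within the assumed range it could not. The fault is a modest upward bias in reported improvement, together with wording in 14.8 that attributes the whole change to treatment.

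**What to change.** 1. In Table 6-2, add a second self-administered IPSS on the procedure day, completed before the pre-medication described in section 6.4. State that it plays no part in eligibility, so nobody is re-excluded on it.
2. In section 5.3.4, name that reading as the Endpoint 4 baseline. Eligibility stays on the screening score.
3. In section 14.8, replace the closing clause about the effect of treatment with *to describe change from baseline*. This is needed even with the new baseline, because placebo response and natural course remain in an uncontrolled change.

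No change is proposed for Qmax. No second pre-treatment void is scheduled, and using one only where it happens to exist would mix two baseline definitions across subjects. A sentence noting that its descriptive change carries the same bias is enough.

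The cost is one extra questionnaire for each of at most 15 men already attending for the procedure, and a slightly smaller reported improvement. The change has to be made before treatment, since a missing pre-treatment score cannot be recovered. It removes the bias fully only if day-to-day variation on the procedure day is independent of that at screening.
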